## Statistical analyses

The statistical analysis will include descriptive statistics reflecting the explorative nature of the study. In general, the data will be presented by dose level in Part 1 and by treatment group in Part 2.

No single primary endpoint has been identified, and there will be no multiplicity adjustments for the statistical analysis comparisons performed. In Part 2, the statistical analyses are based on the assumption that a placebo effect is negligible, so the primary statistical analyses will be performed using analyses of covariance of the change and relative change from baseline in the pharmacodynamic parameters adjusting for the respective baseline values to assess the significance of comparisons with baseline within each group (in the treatment group to assess the treatment effect and in the placebo group to assess the assumption of a negligible placebo effect). Secondary inferential statistics will be computed between placebo and active treatment using an analyses of covariance with treatment group as an additional factor.

The pharmacodynamic and safety endpoints will be analysed for the safety analysis set. The PK analyses will be performed for the PP analysis set.

HVPG will be derived as the average of the duplicate assessments, separately calculated for each scheduled assessment, of the difference between WHVP and FHVP (WHVP- FHVP).

HVPG and other haemodynamic variables will be assessed as change from baseline to 1 and 2 hours post dose separately analysed for each treatment group, and compared between groups.

Non-compartmental pharmacokinetic analysis of FE 204205 will be performed.

Changes in safety parameters will be evaluated by subject listings and descriptive statistics.

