### **3.5 Discussion of Overall Trial Design and Choice of Control Groups**

#### **3.5.1 Trial Design**

The purpose of Part 1 is to assess safety, tolerability, and pharmacodynamics in the dose interval 0.01-0.1 mg i.v. infusion over 2 hours, and thus determine the maximum tolerated dose within this dose interval. Part 1 is open-label since it comprises only one treatment arm, and it was neither regarded necessary nor ethically justifiable to include placebo treatment. The assessment of systemic and portal hemodynamics by pulmonary artery and hepatic vein catheterization on Day 3 will enable a more precise evaluation of the hemodynamic effect at the maximum tolerated dose, compared to non-invasive vital signs assessments.

Part 2 is aiming at defining the anticipated maximal effects of a single intravenous dose of FE 204205 on portal haemodynamics. Part 2 of the trial is randomised and placebo-controlled in order to correct for the non-treatment related factors that otherwise may have an impact on the evaluation of FE 204205. All subjects will be randomly allocated to active treatment or placebo in a double-blind setting, i.e. the active or placebo treatment will not be revealed to the subjects or the personnel involved in the trial. The randomisation is standard procedure in studies with more than one treatment arm.

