### 9.1 Determination of Sample Size

Part 1: No formal sample size calculation has been made. However, the number of patients (six) is considered sufficient to provide adequate information about the safety and tolerability of FE 204205, and thus inform about the suitable dose to evaluate in part 2.

Part 2: Since this is the first exploratory evaluation of the efficacy of FE 204205 on reducing portal pressure, the sample size and power calculations were performed by evaluation of the intra-group difference (before and after treatment with FE 204205). Assuming, based on the literature, a standard deviation (SD) of relative change from baseline of 12 % (see table below), a sample size of 14 patients on active treatment was deemed sufficient to detect a within-group 10 % reduction in HVPG, with  $\alpha = 0.05$  and  $1-\beta = 0.8$ . Taking into consideration that it occasionally can be technically challenging to assess HVPG, a total of 20 patients (16 on FE 204205 and 4 on placebo) are targeted (4:1 randomisation).

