### 9.6.1 General Considerations

All endpoints (see Section 9.6.2) will be analysed using descriptive statistics. In general, the data will be presented by dose level and time point in part 1 and by treatment group and time point in Part 2.

Inferential analyses on change and relative change from baseline in systemic and portal haemodynamic variables from Part 2 of the study will be conducted by using an Analyses of Covariance (ANCOVA) adjusting for the respective baseline value per treatment arm and time point. The focussing on mean change from baseline is based on the assumption the of a negligible placebo effect as reported in e.g. (7,8). Nevertheless, placebo-subtracted treatment effects will also be inferred (despite of limited power) using ANCOVA with treatment group as an additional factor.

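### Part 2 reads the active-arm change from baseline as the treatment effect, and a significance test in 4 placebo patients (2 residual df) cannot check the negligible-placebo assumption behind it

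*Combined protocol and SAP*

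**What the plan says.** Section 3.5.1 explains that Part 2 is "randomised and placebo-controlled in order to correct for the non-treatment related factors that otherwise may have an impact" on the evaluation of FE 204205.

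The synopsis (Statistical analyses) states that "the statistical analyses are based on the assumption that a placebo effect is negligible". It therefore makes the within-group ANCOVA of change and relative change from baseline the primary analysis, and tests significance against baseline in each group: in the active group to judge the treatment effect, and "in the placebo group to assess the assumption of a negligible placebo effect". Section 9.6.1 confirms that the model is fitted separately per arm and time point, adjusting for baseline. It cites references 7 and 8 (a terlipressin study and a simvastatin trial) for the assumption, without giving a figure.

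The controlled comparison is also planned, as secondary: "placebo-subtracted treatment effects will also be inferred (despite of limited power) using ANCOVA with treatment group as an additional factor".

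Section 9.1 sizes Part 2 on the before/after change within the active arm: 14 patients for a 10% HVPG reduction at SD 12%, alpha 0.05 and 80% power. This becomes 16 active and 4 placebo because "it occasionally can be technically challenging to assess HVPG". No power figure is given for the placebo-adjusted comparison. No margin, precision target or reading rule is given for a non-significant placebo result.

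**The concern.** The placebo arm is there to correct for non-treatment factors, but the primary analysis does not use it for that. It relies on the placebo change being negligible, and the only check inside the trial is whether the placebo change reaches significance. Failing to reach significance in 4 patients is not evidence of no change.

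HVPG is read before dosing and at 1 and 2 hours, during a catheter study under sedation. Any change that both arms share over that time goes straight into the active-arm result. A fall would look like a drug effect and a rise would hide one. A significant active change next to a non-significant placebo change could then be reported as a drug effect with its assumption apparently confirmed.

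**Working it through.** **Inputs.** From section 9.1 and Table 9-1: SD of relative change in HVPG 12% (tabulated range 9% to about 14%), target change 10%, alpha 0.05, 16 active and 4 placebo. Assumed here: two-sided testing (section 9.1 does not say, but two-sided reproduces its sample size), the same SD in both arms, and estimates taken at the arm's mean baseline, which is the most favourable case. Points are percentage points of relative change in HVPG. Power is from the noncentral t distribution.

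**1. The plan's own figure.** Paired t-test, noncentrality = (10/12)·√n. Power is 78.8% at n = 13 and 82.2% at n = 14, so the stated 14 reproduces.

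**2. The placebo check.** Residual df = 4 − 2 = 2 and the critical t is 4.303.
- 95% CI half-width = 4.303 × 12/√4 = 25.8 points, about 2.6 times the target effect.
- Noncentrality at a true change of 10 points = 10/(12/√4) = 1.67.

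| SD | CI half-width | Power at 5 points | at 10 | at 20 | Change needed for 80% power |
|---|---|---|---|---|---|
| 9% | ±19.4 | 11% | 25% | 64% | about 25 |
| 12% | ±25.8 | 8% | 17% | 45% | about 34 |
| 14% | ±30.1 | 7% | 14% | 36% | about 40 |

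If one placebo HVPG cannot be read, 1 df remains. The half-width is 12.706 × 12/√3 = 88.0 points, and power at 10 points is 9%.

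**3. What this does to the conclusion.** Suppose the drug is inert and both arms drift by the same amount. The drift sizes are assumptions, because the documents give no placebo change. The active arm has n = 16 and 14 df. The arms are independent, so the last column is P(active significant) × [1 − P(placebo significant)].

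| Shared drift (points) | Active significant | Placebo significant | Active significant, placebo not |
|---|---|---|---|
| 0 | 5.0% | 5.0% | 4.8% |
| 2 | 9.5% | 5.5% | 9.0% |
| 3 | 15.4% | 6.2% | 14.5% |
| 5 | 34.2% | 8.2% | 31.4% |
| 10 | 87.2% | 17.0% | 72.4% |

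A simulation with 40,000 runs per drift (baseline SD of 4 mmHg assumed, change unrelated to baseline) gave 4.7, 9.0, 14.2, 31.6 and 72.4%. In the same runs the joint ANCOVA rejected in 4.8 to 5.1% at every drift.

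**4. The joint ANCOVA already planned.** Residual df = 20 − 3 = 17 and the critical t is 2.110.
- Placebo mean with pooled residual variance: 2.110 × 12/√4 = ±12.7 points. With 3 placebo patients (16 df): 2.120 × 12/√3 = ±14.7.
- Placebo-adjusted effect: SE = 12 × √(1/16 + 1/4) = 6.71, and the half-width is 2.110 × 6.71 = ±14.2 points.
- Power for a 10-point difference is 29% (47% at SD 9%, 23% at SD 14%). Power of 80% is reached only at about 20 points (15.0 at SD 9%, 23.3 at SD 14%).

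**The case against.** The strongest reply is that most of this is disclosed. Part 2 is described as exploratory with no single primary endpoint. The assumption is stated openly and supported by two references. The sample size is tied to the within-group change, and the between-group ANCOVA is planned with its limited power conceded. That stands, and it means that saying the 80% power is within-group largely repeats section 9.1. But the concession in section 9.6.1 concerns the placebo-subtracted contrast. Nothing warns that the placebo-arm test is uninformative; the synopsis presents it as an assessment of the assumption.

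Other points carry some weight:
- The plan does not define success as active significant and placebo not. That pairing is a plausible reading of the two tests, not a stated rule, and the rates in step 3 depend on assumed drifts. With 14 evaluable active patients instead of 16 they are 27.6% at 5 points and 67.7% at 10.
- No placebo SD is given. If it were as low as 5 to 6% (an assumption), power at 10 points would be 56 to 45%. That is better, but still about even odds of missing a placebo change equal to the target effect.
- The pooled interval of ±12.7 is still wider than the 10-point target, and its variance comes mainly from the active arm. It shows the uncertainty honestly, but it cannot show that the placebo effect is negligible. Four placebo patients remain the limit.
- Section 9 defers detail to a separate statistical analysis plan, which is not in the documents. The reading rule may be there, but the protocol text as it stands gives none.

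**Conclusion.** The concern holds. The primary analysis attributes the active-arm change to FE 204205 without using the control, and the planned check would miss a placebo change of 10 points in about 83% of trials at SD 12% (75% to 86% over SDs of 9% to 14%). A non-significant placebo result therefore cannot be used to support the assumption.

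These figures assume two-sided 5% tests, the protocol's SD in the placebo arm, and 4 evaluable placebo patients. The size and direction of any bias in the active-arm result are unknown, because the documents report no placebo change. At zero drift there is no such bias. This should be fixed before analysis, but it does not call for a different trial: both models are already planned, and the between-arm comparison is protected against shared drift.

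**What to change.** - **Synopsis (Statistical analyses) and 9.6.1:** replace the placebo-group significance test with the placebo mean change and its 95% CI, using the pooled residual variance of the joint ANCOVA. State that a non-significant placebo change will not be read as showing a negligible effect.
- **Same sections:** always report the placebo-adjusted estimate with its 95% CI beside the within-active change. Describe the latter as an uncontrolled before/after change, and do not attribute it to FE 204205 on the within-group p-value alone.
- **Section 9.1 and synopsis (Power):** state that the 80% power covers only the before/after comparison. Add that with 16 versus 4 patients and SD 12%, the placebo-adjusted comparison has about 29% power for 10 points and reaches 80% only at about 20 points.

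The cost is wording in these sections and in the statistical analysis plan. No patients, data or models are added. The price is a wider interval and a less favourable power figure beside the headline result, and the pooled CI assumes equal residual variance in the two arms.

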## LIST OF ABBREVIATIONS AND DEFINITION OF TERMS

### List of Abbreviations

AE	Adverse event
ATC	Anatomical therapeutic chemical classification system
CO	Cardiac output
ECG	Electrocardiogram
eCRF	Electronic case report form
EudraCT	European Union Clinical Trial Database
FHVP	Free hepatic venous pressure
FPFV	First patient first visit
GCP	Good clinical practice
GMP	Good manufacturing practice
HVPG	Hepatic venous pressure gradient
ICH	International Conference on Harmonisation
IEC	Independent ethics committee
IMP	Investigational medicinal product
ITT	Intention-to-treat
IVC	Inferior vena cava
LLOQ	Lower limit of quantification
LPLV	Last patient last visit
MAP	Mean arterial pressure
MedDRA	Medical Dictionary for Regulatory Activities
Non-IMP	Non-investigational medicinal product
PAP	Pulmonary artery pressure
PCWP	Pulmonary capillary wedge pressure
PD	Pharmacodynamic
PK	Pharmacokinetic
PP	Per protocol
RAP	Right atrial pressure
SAE	Serious adverse event
SRC	Safety review committee
SVR	Systemic vascular resistance
WHVP	Wedged hepatic venous pressure

## Definition of Terms

### Definition of general terms

Enrolled	When subject and Investigator have signed the Informed Consent form
Included	When the subject has received the first dose of IMP
Pre-dose	Before dosing on a day of dosing
Treatment period	Part 1: Time from start of infusion on Day 1, until 24 hours after the last administration. Part 2: Time from administration until 24 hours after administration

### Pharmacokinetic terms and definitions

AUC	Area under the concentration-time curve to infinity
AUC t	Area under the concentration-time curve from time zero up to time t, where t is the last time point at which the concentration is above the lower limit of quantification
% Extrap AUC	Percentage of AUC that is due to extrapolation from the last measurable concentration
C max	Maximum concentration observed
t max	Time of maximum observed concentration (C max )
CL	Total systemic clearance
CL R	Renal clearance
V z	Volume of distribution associated with the terminal phase
λ z	First-order rate constant associated with the terminal (log-linear) portion of the concentration-time curve
t 1/2	Elimination half-life
MRT	Mean residence time
A e	Cumulative amount of FE 204205 excreted unchanged in the urine

## 1 INTRODUCTION

### 1.1 Background

Complications of portal hypertension, including ascites, hepatorenal syndrome, and variceal bleeding, are leading causes of morbidity and mortality in cirrhosis. Cirrhosis is a common cause of death in adults worldwide. It results in approximately one million deaths per year worldwide, 170 000 per year in Europe, and 35 000 per year in the USA. Cirrhosis is the main indication for 5500 liver transplants each year in Europe (1).

Patients suffering from cirrhotic portal hypertension have an abnormally high splanchnic blood flow due to increased hepatic resistance and splanchnic arterial vasodilation. These circulatory disturbances cause a decrease in the effective arterial blood volume and a compensatory activation of the sympathetic nervous system, the renin-angiotensin-aldosterone system, and the non-osmotic release of vasopressin, which in turn results in fluid retention and renal vasoconstriction (2).

Terlipressin, a full V1A receptor agonist, has been shown to be effective in the management of several complications to cirrhotic portal hypertension (3). Terlipressin reduces the portal pressure and this effect is mediated by an arteriolar vasoconstriction in the splanchnic area. By counter-acting the splanchnic arterial vasodilation and increasing the effective arterial blood volume, thereby improving renal perfusion and glomerular filtration rates, terlipressin has been shown to improve renal function in patients with hepatorenal syndrome (4). There are also reports showing that terlipressin, by normalising the underlying circulatory derangements, is effective in the treatment of refractory ascites (5). The rationale for use of terlipressin for treatment of variceal bleeding is to produce splanchnic vasoconstriction and thereby reduce portal blood inflow and portal pressure, thus decreasing portal-variceal flow and pressure (3).

Existing V1A receptor agonists, such as terlipressin, are full agonists and may produce excessive vasoconstriction if not dosed carefully. The risk profile of V1A full agonists requires careful titration and monitoring to prevent the development of serious adverse events (SAEs) due to tissue hypoxia and ischemia. Thus, the major limitation of existing agents is a risk of excess vasoconstriction, restricting their use to short term applications in inpatient settings under close monitoring by specialists.

FE 204205 is a novel, selective vasopressin 1A receptor (V1A) partial agonist in clinical development intended for the treatment of complications to cirrhotic portal hypertension. FE 204205 have a peptide sequence that comprises one V1A agonist part linked to a V1A antagonist part, resulting in a molecule with partial V1A agonist properties, thereby improving the therapeutic index by a lower maximal effect and lower risk for excessive vasoconstriction. In animal studies FE 204205 shows only approximately half of the maximal vasoconstriction produced by full agonists without any concomitant signs of ischemia (i.e. no increased lactate levels).

Results from two Phase I studies, in which healthy subjects received FE 204205 intravenously, indicated that it acts as a partial V1A agonist, resulting in adequate clinical vasoconstriction

concomitant with the required safety. The maximal effect on vasoconstriction, by means of blood pressure, was reached at a plasma concentration of approximately 1 ng/ml, achieved by an intravenous infusion of 0.1 mg over 6 hours. The effect of FE 204205 appears to be capped compared to a full V1A agonist, since increasing the dose 9-fold (from 0.1 mg to 0.9 mg over 6 hours) did not result in greater pharmacodynamic effects. Administration of 0.9 mg over 6 hours was well tolerated with adverse events (AEs) as expected by a V1A receptor agonist.

Subcutaneous administration of FE 204205 resulted, possibly due to local peptidase activity, in the generation of an active metabolite (M1) at equimolar concentrations to FE 204205. M1 is characterised as a V1A full agonist, and the subcutaneous administration caused more AEs and of higher intensity than intravenous administration, and the maximal tolerated subcutaneous dose of FE 204205 was defined as 0.1 mg. In contrast, after intravenous administration the M1 metabolite was detected only at very low concentrations,  $\leq 2\%$  of the FE 204205, and is not expected to show any appreciable pharmacodynamic effects in this trial.

This is the first study with FE 204205 in patients with cirrhotic portal hypertension and the selected endpoints will focus on the evaluation of safety and tolerability of the treatment in general, the investigation of effects on portal and systemic haemodynamics, and the pharmacokinetics of FE 204205.

## 1.2 Scientific Justification for Conducting the Trial

This is the first study with FE 204205 in patients with cirrhotic portal hypertension, and the selected endpoints will focus on the evaluation of safety and tolerability of the treatment in general, the effects on portal and systemic haemodynamics, and the pharmacokinetics of FE 204205.

It is essential that FE 204205 is administered intravenously, since other routes of administration may cause degradation of the molecule resulting in the generation of the full agonist M1, as shown following subcutaneous administration in healthy subjects. Adequate procedures are in place, according to standard medical practice, to avoid extravasation, i.e. accidental injection or leakage of FE 204205 into the subcutaneous space or perivascular tissues.

The above mentioned risks are addressed in the inclusion and exclusion criteria for the trial and will be closely monitored through safety laboratory evaluations, cardiovascular monitoring including vital signs and ECG, AE reporting, and by safety review committee (SRC) evaluations. The risk posed to the patients participating in the trial is deemed low and ethically justifiable. For more detailed information on FE 204205 please refer to the Investigator's Brochure (6).

## 2 TRIAL OBJECTIVES AND ENDPOINTS

### 2.1 Objectives

- Safety and tolerability of single intravenous infusions of FE 204205
- Pharmacological effect of FE 204205 on systemic and portal haemodynamics in patients with cirrhotic portal hypertension
- Pharmacokinetics of FE 204205 after intravenous infusion
- Relationship between pharmacokinetics and pharmacodynamics of FE 204205
- Metabolites of FE 204205 in plasma and urine of patients
- Exploratory assessment of effects of FE 204205 on soluble biomarkers and renal function variables

[figure not shown]
## 2.2 Endpoints

- Type, frequency and intensity of AEs
- Electrocardiogram (ECG) (intervals, rhythm, and morphology)
- Clinical chemistry, haematology and urinalysis
- Venous blood gases including lactate
- Systemic haemodynamics: Blood pressures and heart rate by non-invasive measurements, pulmonary capillary wedge pressure (PCWP), pulmonary artery pressure (PAP), right atrial pressure (RAP), mean arterial pressure (MAP), and cardiac output (CO) by pulmonary artery catheterization. CO, MAP, and RAP will be used for calculation of the systemic vascular resistance (SVR)
- Portal haemodynamics by hepatic vein catheterization: Free hepatic venous pressure (FHVP), wedged hepatic venous pressure (WHVP), and inferior vena cava pressure (IVC). WHVP and the FHVP will be used for calculation of the hepatic venous pressure gradient (HVPG)
- Pharmacokinetics FE 204205: AUC, AUCt, %extrap AUC, Cmax, tmax, CL, Vz, t1/2, MRT, Ae, and CLR
- Metabolites in plasma and urine
- Blood and urinary biomarkers: Renin, aldosterone, norepinephrine, atrial natriuretic peptide (ANP), brain natriuretic peptide (BNP), urine creatinine, urine sodium, and urine osmolality

[figure not shown]
### 3 INVESTIGATIONAL PLAN

### 3.1 Overall Trial Design

### 3.1.1 Trial Design Diagram

### Figure 3-1 Overall study design for each patient in Part 1

### Figure 3-2 Overall study design for each patient in Part 2

